Whether a patient is in the intervention group or the control will be by random selection using a random number generator in a simple blocked manner (blocks of 8).

Blinding:

This is an open-label study, so subjects and the research team will be aware of the study assignment. Due to the nature of the intervention, blinding of the subject and research staff is unable to be performed. In order to minimize bias, data for outcomes will be collected by a blinded study coordinator.

2.f Risks and Benefits

There are minimal risks to patient safety during the completion of this study within the intervention arm and no risks with regards to study interventions within the control arm. This study will not involve requiring patients to take any experimental medications. All patients, regardless of randomization will receive standard usual care as part of this study. Any adjustments or changes made to the patient's medication regimen in the intervention group will be approved by a transplant physician. There will be increased monitoring and scrutiny of patient's home blood pressures, glucoses and medication regimens. All documented medication errors and adverse drug events will be identified by a blinded research coordinator at the same frequency and methodology across intervention and control patients. This will minimize the likelihood of identifying higher rates of medication safety issues in the intervention group. The risk associated with the intervention arm is in loss of patient confidentiality, which will be mitigated through the use of HIPPA compliant data encryption on mobile devices and storage of PHI on password protected databases behind the MUSC firewall.

Although it is expected that this will improve medication safety, it may also increase stress on patients and increase the potential of identifying false positive information. We will minimize the risk of this causing harm to study patients by ensuring all data is closely monitored by a highly trained clinical pharmacist. All interventions made based on this will be reviewed and approved by a transplant physician.

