8. Costs associated with care will be assessed based on data from hospital accounting at the study institution, once the study is completed. Costs will be measured from the time of randomization up until the end of the 12-month follow-up period. Analyses will include all costs associated with inpatient and outpatient care, including hospitalizations, ambulatory care visits, ambulatory procedure visits, acute care/emergency room visits and laboratory assessments. Costs uniquely associated with the intervention group will include the costs of the devices and data plan provided to the patients, time necessary for training patients on use of the technology and research pharmacist time associated with the intervention. Total costs will be calculated for each cohort. These data will be electronically captured by providing a list of patient's MRNs to hospital accounting after the completion of the study to allow for accurate and complete billing information to accrue. Costs associated with healthcare encounters that occur outside the study institution will be estimated by acquiring information from the patient regarding the type of encounter and using this data to estimate cost based on cost/charge ratios from the study institution. This will be a costs - consequences analysis (CCA) using cost effectiveness methodology, taken from the societal perspective.

F Statistical Plan

F1 Sample Size Determination and Power

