Based on previous studies conducted by our research collaborative, we estimate that approximately 64% of kidney transplant recipients in the control group will experience a medication error during the one year study (defined using the Overhage criteria).(1, 2) Our previous research demonstrates that pharmacist-led initiatives can reduce these medication errors by approximately 50%.(3, 4) Using these estimates, enrolling 104 participants (52 in each cohort), will provide 92% power in detecting a statistically significant difference in medication error event rates, with a two-tailed $\alpha=0.05$. We will also have 94% power (two-tailed, $\alpha=0.05$) to detect a 33% reduction in significant adverse drug events (CTCAE grade 3 or higher), given an estimated incidence rate of 87% in the control cohort and the strong association between medication errors and adverse drug events.(2, 5) From previous analyses, we expect that the control cohort will have a mean of 18.4 ± 2.6 healthcare encounters (clinic visits, acute care/ER visits and hospitalizations), during the one year study. We estimate the intervention group will see an 8% absolute reduction in total encounters, to a mean 17.0 encounters, with an estimated 33% relative reduction in the mean number of hospital readmissions (1.2 vs. 0.8, respectively).(2) Given these estimates (two-tailed, $\alpha=0.05$), enrolling 52 patients in each arm will provide 80% power to detect a statistically significant difference. It is estimated that the intervention will also produce a mean cost savings of at least \$2,489 per patient (\$7,658 in the control cohort and \$5,169 in the intervention cohort, with σ estimated at \$4,530).(2) This study is expected to have >80% power to detect a statistically significant difference in total post-transplant costs between cohorts, given these estimates.

For the exploratory outcomes of acute rejection, infections, graft function, graft loss and death, this study is not powered to detect statistically significant differences in these clinical events between groups. However, we expect to demonstrate meaningful clinical signals, particularly with a reduction in acute rejection. Our previous study demonstrated an acute rejection rate that was 1.8 times higher in patients experiencing a significant medication error (13.7% vs. 7.7%, respectively).(2) Thus, we expect an overall acute rejection rate of 12% in the control cohort and 9% in the intervention cohort,

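### F1's cost power shows no allowance for the intervention-only costs that E4 item 8 charges to the intervention arm; the $2,489 saving appears to be gross, and if so the power for net cost is lower than stated

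*Combined protocol and SAP*

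**What the plan says.** Section F1 (Sample Size Determination and Power) states: "It is estimated that the intervention will also produce a mean cost savings of at least" $2,489 per patient. It gives an expected mean cost of $7,658 in the control arm and $5,169 in the intervention arm, "with σ estimated at \$4,530". It concludes: "This study is expected to have >80% power to detect a statistically significant difference in total post-transplant costs between cohorts". The figures are attributed to earlier work by the group; their components are not listed. The same paragraph assumes a "33% relative reduction in the mean number of hospital readmissions (1.2 vs. 0.8, respectively", and a fall in total encounters from 18.4 to 17.0.

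Section E4 item 8 defines the cost endpoint as all inpatient and outpatient care, from a societal perspective. It then adds items for one arm only: "Costs uniquely associated with the intervention group will include the costs of the devices and data plan provided to the patients", together with time spent training patients and research pharmacist time. No dollar amount is given for any of these.

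Section D2 2.f says of the pharmacist's monitoring: "All interventions made based on this will be reviewed and approved by a transplant physician". The intervention-only list in E4 item 8 names neither that physician time nor the app and telemonitoring platform described in section D3 3.a.

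**The concern.** The cost comparison will be made on totals that include the intervention's own costs. If the $2,489 in F1 is the saving before those costs, the difference that was powered is larger than the difference that will be tested, and the claim of more than 80% power does not carry over to the planned analysis. Reduced cost is part of Hypothesis 2, which section A2 lists under the primary hypothesis.

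A second, smaller issue concerns the endpoint itself. Physician review and the platform are resources that only the intervention arm uses. If they stay out of the total, the reported saving leans towards the intervention.

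**Working it through.** **Inputs.** From F1: mean costs $7,658 and $5,169; SD $4,530; readmissions 1.2 and 0.8; total encounters 18.4 and 17.0; 52 per arm and two-sided alpha 0.05 (both stated for the encounter comparison and assumed here to apply to cost); 85% retention of 136 enrolled. Completers per arm: 136 × 0.85 / 2 = 57.8, about 58. Enrolled per arm: 68. The intervention cost per patient, c, is not in the documents and is assumed.

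**1. Reproducing F1.** The difference is 7,658 − 5,169 = $2,489. At 52 per arm the standard error is 4,530 × √(2/52) = $888, and 2,489 / 888.4 = 2.80. The normal approximation gives Φ(2.80 − 1.96) = 80.0%; the noncentral t gives 79.3%. At 58 and 68 per arm the t-based power is 83.5% and 88.9%. F1's figure therefore reproduces on its own inputs, with no slack at 52 per arm.

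**2. Does the saving look gross or net?** Cost falls by 2,489 / 7,658 = 32.5%. Readmissions fall by 0.4 / 1.2 = 33.3%, and total encounters by 1.4 / 18.4 = 7.6%. If cost fell exactly in proportion to readmissions, the saving would be 7,658 × 0.4 / 1.2 = $2,553. That is $64 above the stated saving, a gap of less than 3%.

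The counts can be used more fully. Encounters other than readmissions are 18.4 − 1.2 = 17.2 and 17.0 − 0.8 = 16.2. Let R be the cost per readmission and O the cost per other encounter, the same in both arms:

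- Control: 1.2R + 17.2·O = 7,658
- Intervention: 0.8R + 16.2·O + c = 5,169

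Two-thirds of the first equation is 0.8R + 11.467·O = 5,105.33. Subtracting it from the second gives 4.733·O + c = 63.67. Since O cannot be negative, c is at most about $64 per patient, and reaches that only if every other encounter is free. With c = 0, O is about $13 per encounter. Section D3 3.a describes weekly pharmacist telemonitoring, home monitors, and a device and data plan for patients without an iPhone; $64 spread over 52 weekly reviews alone is $1.23 each.

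A larger c requires avoided readmissions to cost more than average ones. At c = $500 with free outpatient care, each avoided readmission would have to cost (2,489 + 500) / 0.4 = $7,473, against a highest possible average of 7,658 / 1.2 = $6,382, or 17% more. F1 states no such assumption.

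**3. Power if the saving is gross.** Two-sample t-test, noncentrality (2,489 − c) / (4,530 × √(2/n)), SD held at $4,530:

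| Assumed c per patient | Net difference | 52 per arm | 58 per arm | 68 per arm |
|---|---|---|---|---|
| $0 | $2,489 | 79% | 83% | 89% |
| $250 | $2,239 | 70% | 75% | 82% |
| $500 | $1,989 | 60% | 65% | 72% |
| $1,000 | $1,489 | 38% | 42% | 48% |

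The smallest difference detectable with 80% power (normal approximation) is $2,489 at 52, $2,357 at 58 and $2,177 at 68 per arm. Power therefore drops below 80% for essentially any positive c at 52 per arm, above about $132 at 58, and above about $312 at 68.

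**The case against.** A reader might infer that the $2,489 equals the cost of the avoided readmissions, that it nets off none of the intervention's cost, and that F1's power is therefore wrong. The documents do not support that. F1 gives no cost per readmission and no component list. Dividing $7,658 by 1.2 presumes that the whole total is readmission cost, whereas F1 calls it total post-transplant cost. The match is approximate, not exact. The only readmission cost in the documents, a median of $18,091 in Table 1 for patients with a clinically significant error, is not a unit cost, and 0.4 × 18,091 = $7,236 is far from $2,489. F1 also presents its saving as a minimum, and its arithmetic is sound on its own inputs. All of this stands, so the gross reading remains an inference and the size of any shortfall is conditional.

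The power table has limits too. Section F3 plans intention-to-treat analysis with multiple imputation, and institutional costs come from hospital accounting, so the analysed number may exceed 58 per arm. Because section D2 2.i stops data collection at full withdrawal, 68 is an upper bound. F3 also calls for the Mann-Whitney test when data are not normal, and the readmission costs in Table 1 are skewed, so t-test power is only a guide.

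On the omitted items, the E4 list is not worded as exhaustive, and section C2 includes staff effort among the resources to be measured. That narrows the point but does not remove it: C2 does not place physician time or the platform in the cost total, and hospital accounting is unlikely to capture unbilled remote approvals.

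**Conclusion.** The point holds in conditional form. F1 shows no allowance for costs that E4 item 8 adds to one arm. With equal unit costs in both arms, its own counts leave room for at most about $64 per patient, so the figure is very likely gross. If it is, the claim of more than 80% power fails at 52 per arm for essentially any positive intervention cost, at about 58 completers once that cost passes about $132, and even at the enrolled 68 once it passes about $312. These thresholds rest on an SD of $4,530 also applying to the E4 endpoint and on a comparison of means. The actual loss of power cannot be stated until the sponsor supplies an intervention cost. Separately, the intervention-only cost list is incomplete for an analysis taken from a societal perspective, in a direction that favours the intervention.

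**What to change.** In F1, state which components the $7,658, $5,169 and $4,530 contain. If they are gross, subtract a budgeted per-patient intervention cost and restate the power for the net difference at 52, about 58 and 68 per arm. No added enrolment is proposed.

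In E4 item 8, add two items to the intervention-arm costs: transplant-physician review time (logged recommendations × a fixed unit time and wage) and a per-patient cost for the app and telemonitoring platform. Report gross and net savings side by side.

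The cost is a change of wording in two sections, one recalculation and minor extra costing work; televisits are already documented in the health record, which gives a source for the count of recommendations. The downside is that the stated power and saving become less favourable.

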This analysis will incorporate the intent-to-treat principle, namely, all randomized participants will be included in the analysis according to their intervention assigned at baseline. The two groups will be compared using standard statistical analyses. Data will be reported using percentages for nominal and ordinal variables and compared using Fisher's exact test or Pearson's chi-squared test as appropriate. This includes baseline demographic and transplant characteristic variables, as well as the outcome variables of the incidence and severity of medication errors and adverse drug events, acute rejection and infections. For continuous variables with normal distribution, results will be reported using means and standard deviations with statistical comparison using Student's t-test for two independent samples. For *non-normally distributed* variables, the results will be reported using medians and interquartile ranges, with statistical comparison conducted using the Mann Whitney U test. Normal distribution of continuous variables will be assessed using normality plots and the Shapiro-Wilk test. Normal variance will be assessed using Levene's test for equality of variances. Results for graft and patient survival will also be reported using Kaplan-Meier survival curves and compared using the Log Rank test.

If it is determined that there are significant imbalances in baseline demographics or characteristics known to influence any of the outcome measures, multivariable modelling will be used to adjust for these differences. For nominal outcomes, binary logistic regression will be used in a standard entry fashion, which will include both the grouping variable and all known risk-factors. For continuous outcomes that demonstrate linearity

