in the relationship between dependent and independent variables, with a lack of serial correlation between covariates, homoscedasticity of the errors and normality of the error distribution, linear regression will be utilized in a similar manner. We will adjust for baseline values if the interventions are discrepant at baseline. This model will include the intervention arm and baseline response as fixed-effects and is known to lead to very precise inference.(7) If any of the four aforementioned assumptions are violated, then the data variables will either be transformed or appropriate substitute multivariable modelling will be used. Cox proportional hazard regression analysis will be used for time-dependent survival analyses involving the outcomes of graft and patient survival. For count outcomes, such as health care encounters, we will use Poisson regression; if the assumption of equal mean and variance is violated (over dispersion), we will use Negative Binomial regression. In all models, we will adjust for correlation of outcomes by including random effect terms. For all models that belong to the generalized linear model (linear, logistic, Poisson), we will use generalized estimating equations (GEE), and for survival outcomes, we will use frailty Cox regression.(8) We will use multiple imputation techniques to deal with missing data that is at random (MAR).(9) MAR assumes that the probability that an outcome is missing depends on observed outcomes. While mechanisms for missingness are likely to be MAR, we will also do sensitivity analysis for data missing not at random (MNAR) using methods from Little and Rubin.(9)

F4 Statistical Methods

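### F1 powers a mean cost saving, but F3 and F4 send skewed costs to medians and Mann-Whitney and name no inference for the mean; the encounter analysis also needs one named method

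*Combined protocol and SAP*

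**What the plan says.** Costs:

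- F1 plans on means. "It is estimated that the intervention will also produce a mean cost savings of at least" $2,489 per patient ($7,658 control, $5,169 intervention, σ $4,530), with power above 80%.
- E4, item 8, describes the economic analysis: "This will be a costs - consequences analysis (CCA) using cost effectiveness methodology, taken from the societal perspective". It adds intervention-only costs ("Costs uniquely associated with the intervention group will include the costs of the devices and data plan provided to the patients", plus training and pharmacist time) and states that "Total costs will be calculated for each cohort".
- F3, repeated in F4, compares normally distributed continuous variables by t-test. For the others, "the results will be reported using medians and interquartile ranges, with statistical comparison conducted using the Mann Whitney U test". Normality is judged by plots and the Shapiro-Wilk test. Cost is not exempted.
- In F3's multivariable modelling, if the linear-model assumptions fail, "the data variables will either be transformed or appropriate substitute multivariable modelling will be used". No substitute model is named.

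Encounters:

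- F1: "we expect that the control cohort will have a mean of 18.4 ± 2.6 healthcare encounters", against 17.0 in the intervention arm, with 80% power at 52 per arm.
- F3: "For count outcomes, such as health care encounters, we will use Poisson regression; if the assumption of equal mean and variance is violated", with overdispersion named in brackets, the analysis moves to Negative Binomial. F3 then asks for random effects in every model and for GEE in the linear, logistic and Poisson models. It does not say which standard errors apply.

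**The concern.** The sample size section and the analysis section do not target the same quantity for cost. A payer or hospital needs the mean cost per patient, because the mean times the number of patients is the budget effect. A rank test with medians neither tests nor estimates that mean. E4's cohort totals would yield arm means, but no section attaches a test or an interval to their difference.

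For encounters, F1's SD implies counts less variable than Poisson, while F3's only fallback is for counts more variable than Poisson. F3's sentences on random effects and on GEE can lead to different standard errors, and so to different conclusions from the same data.

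Both matters belong to Hypothesis 2, which C2 treats as a secondary aim. The primary outcome of medication errors and adverse drug events is not affected.

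**Working it through.** **Inputs.** From F1: the means, SDs and 52 per arm given above, two-sided α 0.05. F1 gives one cost σ, used here in both arms, and an encounter SD for control only, assumed equal in both arms. From F1: 68 randomised per arm with 85% retention, so 68 × 0.85 = 57.8, about 58 completers. From Table 1 in B1: readmission costs in an earlier cohort.

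**1. F1's figures.** Power ≈ Φ(δ/σ × √(n/2) − 1.96), with √(52/2) = 5.099.

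- Costs: 2,489/4,530 = 0.549; 0.549 × 5.099 = 2.80; less 1.96 is 0.84; Φ = 80%. By noncentral t: 79% at 52 and 83% at 58.
- Encounters: 1.4/2.6 = 0.538; 0.538 × 5.099 = 2.75; less 1.96 is 0.79; Φ = 78%. By noncentral t: 78% at 52 and 82% at 58. Without rounding the 8% reduction (0.08 × 18.4 = 1.472), power at 52 is 82%.

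Both figures reproduce, to rounding, as comparisons of two means.

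**2. Is the rank branch likely for costs?** Under normality, the share of costs below zero would be Φ(−5,169/4,530) = Φ(−1.14) = 12.7% in the intervention arm and Φ(−7,658/4,530) = Φ(−1.69) = 4.5% in control. Costs cannot be negative, so the distribution must be skewed. Table 1 agrees: readmission costs had a median of $18,091 (IQR $3K to $56K) with a clinically significant error and $0 (IQR $0 to $16K) without an error. In 4,000 simulated trials at 52 per arm, with F1's means and σ and an assumed gamma or lognormal shape, Shapiro-Wilk rejected normality in at least one arm in over 99.9%.

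**3. What the rank branch reports.** For a lognormal, median = mean/√(1 + CV²). The CVs are 4,530/7,658 = 0.592 and 4,530/5,169 = 0.876. The medians are 7,658/1.162 ≈ $6,591 and 5,169/1.330 ≈ $3,887, a difference of about $2,704. For a gamma, numerical medians are $6,786 and $3,922, a difference of about $2,860. The mean difference is $2,489 in both cases.

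| Assumed shape, 52 per arm | Welch t | Mann-Whitney |
|---|---|---|
| Gamma | 79% | 93% |
| Lognormal | 80% | 98% |

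Sensitivity: if the CV rather than σ is held constant across arms (a departure from F1), the median difference is about $2,130 to $2,190, with Mann-Whitney power 87% to 94% and t-test power 91% to 92%. The median difference can therefore lie on either side of the mean saving.

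**4. Encounters.** Variance/mean = 2.6²/18.4 = 6.76/18.4 = 0.37. On the log scale the effect is ln(18.4/17.0) = 0.0791. At 52 per arm:

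- Model-based Poisson error: √(1/(52 × 18.4) + 1/(52 × 17.0)) = 0.0467.
- Error implied by SD 2.6: 2.6 × √(1/(52 × 18.4²) + 1/(52 × 17.0²)) = 0.0289.
- Power with model-based errors: Φ((0.0791 − 1.96 × 0.0467)/0.0289) = Φ(−0.43) = 33%.
- Power with robust errors: Φ(0.0791/0.0289 − 1.96) = Φ(0.78) = 78%.

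At 58 per arm the same formulas give 39% and 82%. With no true effect, model-based errors reject in about 0.1% of trials instead of 5%. A Poisson random intercept does not help, because it can only add variance: fitted to 150 simulated trials, its estimated SD was essentially zero in each.

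The ratio 0.37 applies to complete 12-month counts. If 15% withdrew uniformly over the year (an assumption), follow-up T would have mean 0.925 and variance 0.0444. Raw control counts would then have variance 18.4² × 0.0444 + 6.76 × 0.925 ≈ 21.3 on a mean of 17.0, a ratio of 1.25.

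**The case against.** **Costs.** A2 speaks only of reduced costs, and F1's power statement is for a difference in total costs, so the mean could be called a planning input. Planning by t-test and switching to ranks for skewed data is a common convention. E4's totals would also let a reader work out arm means. All of this is fair, and it narrows the point to the absence of named inference on the mean. It does not remove it: F1's effect is a mean saving, and a median difference is not a substitute.

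A reader might infer that Mann-Whitney would cost the trial power or could hide the saving. The documents do not support that. With F1's means and σ, ranks have more power than a mean comparison under the simple skewed shapes tried. A large loss appears only with cost components and arm-specific SDs that the documents do not give and that partly conflict with F1's σ.

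**Encounters.** A reader might infer that the encounter comparison has only about one-third power. That holds only if the random-effects sentence overrides the one assigning Poisson models to GEE. GEE is normally run with robust errors, which restores about 78% to 82%. The count rule also sits in text introduced for baseline imbalance. If it covers only that case, the main test is the t-test or Mann-Whitney (77% and 74% at 52 per arm in simulation), and the loss does not arise. What stands is an inconsistency to reconcile, not a demonstrated loss of power.

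**Conclusion.** The cost point holds. As written, the plan will almost certainly compare costs by medians and ranks, and it provides no inference on the $2,489 mean saving that F1 powers. Under F1's means and σ the reported median difference would be about $2,700 to $2,860; this rests on an assumed gamma or lognormal shape, since the documents give only means and one σ. The defect is the quantity estimated, not power.

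The encounter point is lesser. F3 allows more than one analysis, and at the expected 58 completers the choice of standard error separates 39% from 82% power, assuming complete counts with SD 2.6 in both arms. Under the more usual readings there is no loss.

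Both are worth correcting before analysis because the wording is cheap to change and the choice should not be made after seeing the data.

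**What to change.** - **F3 and F4, costs.** State that total cost per patient, including intervention-only costs, is compared between arms as arithmetic means with a bootstrap 95% confidence interval, whatever the distribution. Keep medians and interquartile ranges as description and Mann-Whitney as supportive only.
- **F3, encounters.** Name Poisson GEE with robust (sandwich) errors as the encounter analysis, whatever the direction of dispersion, and remove the random-effects wording for it.

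The cost is a few sentences and no extra patients. The mean comparison has less power than ranks under simple skew (about 80% against 93% to 98% at 52 per arm), which is the price of testing the mean saving. In simulated gamma costs, the percentile bootstrap had 94% coverage and 80% power. Robust errors are slightly liberal at this size (5.7% false positives at 52 per arm in simulation).
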